2. To identify patient and physician behaviors associated with GERD symptom improvement.

Design and Outcomes

This is a randomized controlled trial to assess the physiologic and behavioral mechanisms associated with augmented medication effects in adult patients with functional GERD-related symptoms.

Subjects will be randomized to receive one of two different semi-scripted visit types – either a “standard visit” modeled after an empathic, conventional primary care evaluation or an “expanded visit” modeled after an integrative medicine consultation. During the visit, we will measure heart rate variability (HRV) and galvanic skin response (GSR) in the patient-provider dyads; in addition, we will video record the interactions for later

analysis of behavioral responses. Subjects will receive a two-month supply of amitriptyline (10 mg/day) or omeprazole (20 mg/day, depending upon the nature of their GERD symptoms), along with instructions for taking it. Following the visit, subjects will complete questions assessing their relationship/rapport with the study provider. Subjects will complete a daily GERD symptom diary during the first and eighth weeks of the study. At the end of the 8-week observation period, they will complete follow-up measures of GERD symptom severity and quality of life.

Interventions and Duration

Subjects will have a single visit with a “study provider,” a physician or nurse practitioner who they have never previously met. Subjects will complete a daily symptom diary for the 1st and 8th weeks following this visit and return for a second study visit in which they will complete questionnaires and be debriefed by a member of the study team.

Sample Size and Population

We plan to enroll 60 subjects with functional GERD, age 24-70 with heartburn symptoms 3 or more days per week. Thirty subjects will be randomized to the expanded visit intervention and 30 subjects will be randomized to the standard visit intervention (1:1 expanded vs. standard randomization). We will also enroll approximately 5-6 physicians or nurse practitioners and stratify randomization by study provider such that each provider will see 10-12 subjects (5-6 expanded visits and 5-6 standard visits).

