6. STUDY PROCEDURES

6.1 Schedule of Evaluations for Subjects/Patients

Assessment	Telephone Screening: (Day -30 to -7)	Baseline, Enrollment, Randomization: Visit 1 (Day 0)	Post Intervention: Visit 1 (Day 0)	Follow-up: Visit 2 (Day 53 - 60)
Screening Form	X	X		
GERD Daily Symptom Diary Reviewed		X		X
Informed Consent Form		X		
Current Medication List		X		X
Height and weight		X		
Demographics & Health Behaviors		X		
Blood Draw (optional)		X		X
GERD-Health Related Quality of Life Questionnaire (GERD-HRQL)		X		X
Patient Reported Outcomes Measurement Information System (PROMIS) GERD		X		X
Gastrointestinal Symptom Rating Scale (GSRS)		X		X
Perceived Stress Scale-10 (PSS-10)		X		X
Current Stress Question		X	X	X
NEO Five Factor Inventory (NEO-FFI)		X		
Randomization		X		
HRV, respiratory rate, skin temperature, and GSR		X		
Video recording		X		
Study visit		X		
Impressions of the Study Physician			X	
Consultation And Relational Empathy questionnaire (CARE)			X	
HEAL Patient-Provider Connection			X	
Adverse Events				X
Debriefing				X

Schedules of Evaluations for Providers

Assessment	Enrollment	Prior to each subject/patient encounter	After each subject/patient encounter	After the last study visit
Informed Consent Form	X			
Interpersonal Reactivity Index (IRI)	X			
NEO-FFI	X			
Demographics	X			
Intervention Training	X			
PSS-10		X		
Current Stress Question		X		
Fatigue Scale		X		
Physician Satisfaction Questionnaire			X	
Interview at completion of study				X

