6.2.3 Enrollment, Baseline, and Randomization (Visit 1, Day 0)

Potential subjects will be rescreened using the pre-screen form by a study physician. The study physician will also review the baseline symptom dairy to ensure that the individual is symptomatic enough to enroll. If the individual is eligible to participate in the study, they will be given a copy of the consent form to review.

Consenting Procedure and Enrollment

Written informed consent will be obtained by a study team physician (see also section 4.3). The subject will be given adequate time to read the consent form, and any questions the subject has will be answered. The study team physician will confirm that the subject understands that he/she will be connected to physiologic monitors during the visit and that the visit will be video recorded. The physician will also discuss the risks and benefits of taking amitriptyline or omeprazole. The subject will also have the opportunity to choose whether or not to consent to blood draws as part of the study which will involve one blood draw at the first visit and one blood draw at the second visit. The subject will receive a copy of the consent form and the original signed copy will be kept in a study binder. If the subject agrees to participate and signs the informed consent form, they will be considered "enrolled".

Study providers will be consented by the study PI, following a similar process, using a different written informed consent form.

Baseline Assessments

Evaluations for study participants/patients (self-administered questionnaires take about 15-25 minutes to complete):

- Current medication List – will be pulled from Epic and verified with the patient by a study team physician
- Height and weight – will be obtained by a study team member.
- Demographics and health behaviors – will access things such as age, gender, race/ethnicity, smoking status, alcohol & caffeine use (see Appendix D)
- Blood draw (optional) – 10 mL of blood will be obtained by a trained study staff member or phlebotomist. Blood will be processed to obtain RNA, DNA, and plasma then frozen at -80°C for later omics analyses.

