- Baseline Symptom Diary – 7-day diary indicating the frequency and severity of 9 different GERD and dyspepsia-related symptoms on a 5-point scale as well as any medications, supplements, or other products used to help manage symptoms. The first 3 symptoms (daytime heartburn, nighttime heartburn, and acid reflux) will be used to assess severity of GERD symptoms.
- GERD-HRQL – a validated 11 item scale for assessing the impact of GERD symptoms on health-related quality of life⁷³.
- NIH PROMIS GERD scale – a validated 13 item instrument assessing frequency and severity of GERD symptoms over a 7-day recall period²⁶.
- GSRS: The Gastrointestinal Symptom Rating Scale is a validated 15 item instrument for measuring the severity of gastrointestinal symptoms⁷⁴. It contains 5 subscales: abdominal pain, reflux syndrome, diarrhea syndrome, indigestion syndrome, and constipation syndrome.
- Current Stress Question – 1 item self-report measure of current stress level on a scale of 0 (no stress) to 10 (extreme stress)
- Perceived Stress Scale (PSS) – a widely used 10 item measure of perceived stress that has been shown to correlate with a variety of different health outcomes⁷⁵. We have adapted the originally validated measure to ask about stress over the past week (7 days), rather than the past month, to better fit the timeframe of the study. We have used this timeframe in other studies.
- NEO Five Factor Inventory (NEO-FFI) – a validated 60 item instrument that measured five major dimensions of personality: extraversion, neuroticism, agreeableness, conscientiousness, and openness to experience⁷⁶. Some dimensions have been associated with response to enhanced patient-provider interactions in others' studies⁷⁷.
- Physiologic Measures and Video Recording: During the intervention we will measure HRV, respiratory rate, skin temperature, and GSR in both study patients and study providers. The study visit will also be video recorded. During the COVID-19 pandemic, in order to allow us to collect physiologic and nonverbal behavior data (e.g., smiles) with the patient and physician unmasked, while also complying with institutional and state public health guidelines, the patient and doctor will sit in separate but adjacent, exam rooms with the door closed and use a video telehealth platform (e.g., Zoom, Cisco Meeting) to communicate. We will use the recording function to capture video data.

Evaluations for study providers:

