- Interpersonal Reactivity Index (IRI) – a validated 28 item self-assessment of cognitive and affective components of empathy⁷⁸.
- NEO Five Factor Inventory (NEO-FFI) – a validated 60 item instrument that measures five major dimensions of personality: extraversion, neuroticism, agreeableness, conscientiousness, and openness to experience [73]. Some dimensions have been associated with response to enhanced patient-provider interactions in others' studies⁷⁷.
- Demographics and practice – will assess things such as age, gender, race/ethnicity, and clinical experience (see Appendix D).
- Current Stress Question – 1 item self-report measure of current stress level on a scale of 0 (no stress) to 10 (extreme stress). Study providers will complete this question immediately prior to each study subject visit.
- Perceived Stress Scale (PSS) – a widely used 10 item measure of perceived stress that has been shown to correlate with a variety of different health outcomes⁷⁵. Study providers will complete this questionnaire immediately prior to each study subject visit.
- Fatigue Scale – 1 item self-report measure of the current fatigue level on a scale of 0 (no fatigue) to 10 (extreme fatigue). Study providers will complete this question immediately prior to each study subject visit.
- Physician Satisfaction Questionnaire (PSQ) – 20 item self-report measure assessing physician satisfaction with the patient visit. This measure includes a global satisfaction question and 19 items assessing 4 other domains: satisfaction with the patient-physician relationship, with the data collection process, with the appropriateness of the use of time, and with the absence of excessive demands on the part of the patient. Study providers will complete this questionnaire immediately after each study visit⁷⁹.

Randomization

Subjects will be randomized on the day of their baseline visit (Visit 1) to receive either the standard or expanded visit with the specific provider that they are scheduled to see that day. We will stratify randomization by provider so that each provider does the same proportion of standard and expanded visits. Randomization will occur during or immediately after subjects have completed their baseline questionnaires, immediately prior to the study visit.

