7. SAFETY ASSESSMENTS

Expected risks to subjects are as follows:

- Study questionnaires: Symptom and behavioral data collection involves virtually no risk; however, psychosocial tests or questions about symptom intensity may cause minor emotional distress. Because participants are free to stop at any time and will be reminded of this throughout the assessment process, the risk of distress is low. In our experience, such questionnaires are well-tolerated and complications are extremely rare.
- Discomfort from ECG/GSR leads and physiologic monitoring: Some participants may experience minor skin irritation due to the adhesive used to apply leads for physiologic monitoring. Subjects with known adhesive allergies will not be eligible to participate in the study. Some participants may experience psychological distress knowing that their physiology is being monitored. The physiologic monitoring will be described in the consent document and care will be taken to minimize such distress. Participants will be free to stop at any time. In general, such monitoring is well-tolerated.
- Discomfort from blood draws: some participants may have an aversion to needles, blood, and/or the drawing of blood. Blood will be drawn by trained study staff or phlebotomists and care will be taken to minimize discomfort to participants. Blood draws are generally well-tolerated, although occasionally there may be bruising or discomfort at the site. Rarely an infection can occur. The blood draw will be an optional component of the study, and if an enrolled subject consents to the blood draw and is particularly challenging to draw blood from, we cancel the blood draw and will not require a successful blood draw to be a condition of continued enrollment in the study.
- Videotaping: Some participants may experience psychological distress knowing that they are being videotaped. Participants will be free to stop at any time. In general, videotaping is generally well-tolerated.

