9. STATISTICAL CONSIDERATIONS

9.1 General Design Issues

Design: This is a single-blinded randomized controlled trial in which subjects will be randomized in a 1:1 fashion to receive either an expanded or standard visit with a healthcare provider about their GERD symptoms and then treated with amitriptyline or omeprazole for 8 weeks to determine whether an expanded visit can augment the effects of a medication compared to a standard visit.

Primary hypotheses:

1. Subjects who receive an expanded visit will have a greater improvement in their GERD symptoms after 8 weeks of treatment with amitriptyline or omeprazole compared to subjects who receive a standard visit.

Secondary hypothesis:

1. Patient-provider dyads in expanded visits will have a greater percentage of the total visit time spent in physiologic concordance (measured by either GSR or HRV) compared patient-provider dyads in standard visits.
2. Percentage of visit time with physiologic concordance (in GSR or HRV) will be correlated with GERD symptom improvement.
3. Subjects who experience physiologic changes similar to those elicited by mind-body techniques (i.e., decreased GSR and increased high frequency HRV) over the course of their visit (first several minutes compared to the last several minutes of the visit) will demonstrate greater improvements in GERD symptom severity than subjects who do not.

4. Healthcare providers in expanded visits will demonstrate more patient-centered non-verbal behaviors (e.g., smiles and gazes) and global impression (e.g., engaged, friendly, relaxed) compared to providers in standard visits as rated by blinded reviews of thin slices of video excerpts.
5. Patient and provider smiling at the end of study visits will be significantly associated with GERD symptom improvement 8 weeks later.

Primary outcome:

1. Change in the average daily GERD symptom severity score from baseline to the last week of the study in the expanded vs. standard group. GERD symptom severity is based on the sum of scores assessing the severity of daytime heartburn, nighttime heartburn, and acid reflux each on a 0-4 point scale (none, mild, moderate, severe, very severe; higher scores signify worse symptoms).

Secondary outcomes:

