9.5.2 Secondary Outcomes

1. To analyze physiologic synchrony in GSR, first, an average slope of the GSR will be calculated in the patient and provider recordings in moving 5 second windows, offset by 1 second. Next, Pearson correlations with lag zero will be calculated over successive 15 second windows between time-locked patient and provider GSR slope values. Then, a single session index will be calculated from the ratio of the sum of the positive correlations across the entire visit divided by the sum of the absolute value of the negative correlations across the entire visit. To reduce skew, the natural logarithm of the index will be calculated. Thus, an index value of zero reflects equal positive and negative correlations, a value greater than zero reflects more concordance in GSR than not, while a value less than zero reflects less concordance in the dyad (less than 50%)⁸². These index values will be used in GLM analyses with GERD symptom severity and/or correlated with visit type.

We will also perform similar analyses on the HRV data – comparing variation in the beat-to-beat intervals over short segments of time and calculating Pearson correlation coefficients for time-locked patient and provider data for these intervals.

2. We will calculate absolute changes in both GSR and also high frequency HRV within study subjects from the beginning to the end of the study visit. We will assess the Pearson correlation between these changes and reported changes in GERD symptom severity. We will also look at absolute levels of GSR and HRV at the end of the study visit and compare those values with changes in GERD symptom severity in GLM models. As an exploratory analysis, I will test whether changes in GSR and HRV are a function of baseline perceived stress and if that relationship differs between the standard and expanded visit interventions.
3. To analyze study visit videos, 2 minute thin slices of each video at three time points (beginning, middle, and end of study visits) will be analyzed by trained and blinded coders, for the presence of 1) micro-level non-verbal supportive behaviors (e.g., gazes, smiles, nods, gestures – measured as absolute number or

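### GSR and HRV have no recording from before the randomised visit, so secondary outcome 2 cannot tell relaxation from the fading of a start-of-visit reaction

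*Combined protocol and SAP*

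**What the plan says.** All statements on timing put the recording within the visit. The Précis says "During the visit, we will measure heart rate variability (HRV) and galvanic skin response (GSR) in the patient-provider dyads". Section 6.2.3 says "During the intervention we will measure HRV, respiratory rate, skin temperature, and GSR in both study patients and study providers", and its consent paragraph has the physician confirm that the subject understands that "he/she will be connected to physiologic monitors during the visit". In the section 6.1 schedule, the row "HRV, respiratory rate, skin temperature, and GSR" carries a single mark, in the Visit 1 column that also holds randomisation, video recording and the study visit. It has none under Post Intervention or Visit 2. Section 6.2.3 places randomisation directly before the visit.

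The change is defined from the same recording. Secondary hypothesis 3 in section 9.1 compares the "first several minutes compared to the last several minutes of the visit", and section 9.5.2 item 2 plans "absolute changes in both GSR and also high frequency HRV within study subjects from the beginning to the end of the study visit". The main analysis is a Pearson correlation of this change with the change in GERD severity. The same item also plans GLMs relating end-of-visit levels of GSR and HRV to the change in GERD severity.

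Section 7 acknowledges that "Some participants may experience psychological distress knowing that their physiology is being monitored", and says the same of videotaping.

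**The concern.** Hypothesis 3 is about a particular kind of change: lower GSR and higher high-frequency HRV, of the sort that mind-body techniques produce. Its reference is the first few minutes with a provider the subject has never met, while wired and filmed. If GSR rises or HRV falls at that moment and then recovers, the recovery has the same sign as relaxation and is counted as such. Conversely, any calming that occurs at first contact is already in the reference and is subtracted out.

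At stake is the interpretation of one mechanistic secondary outcome. If the change correlates with symptom improvement, the data cannot show whether improvers relaxed more or simply reacted more at the start. The gap can be closed only during data collection, because a segment that was not recorded cannot be recovered later.

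**Working it through.** The documents state no power or precision for GSR or HRV, so there is no figure of the plan's own to reproduce here. The detectable differences in section 9.2 concern the GERD score and do not bear on this point.

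**1. What the planned change measures.** For one patient and one signal, let B be the level before contact with the provider, S the mean over the first minutes and E the mean over the last minutes. Then

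E − S = (E − B) − (S − B).

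The first term on the right is the response from before the visit to its end; the second is the reaction to its start. The plan records S and E but not B. Two patients make the point, in arbitrary GSR units:

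- Patient 1: B = 10, S = 10, E = 8. Planned change −2; pre-visit-to-end change −2; start reaction 0.
- Patient 2: B = 8, S = 10, E = 8. Planned change −2; pre-visit-to-end change 0; start reaction +2.

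They have the same S and the same E, so no analysis of S and E can tell them apart. Adjusting for S does not help, because S already contains the start reaction.

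**2. What the end-level analysis adds.** It uses E = B + (E − B). S is not involved, which is a real advantage. Without B, however, it mixes stable differences between people with response to the visit.

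**3. Whether a pre-visit value exists elsewhere.** The schedule column is headed as baseline and the procedure entry sits under baseline assessments, but the entry itself states that measurement takes place during the intervention. No resting or acclimatisation segment is described. By contrast, the section 9.5 table has the Current Stress item collected both before and after the provider visit.

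**4. Whether the size can be computed.** It cannot. An illustration shows how far the answer depends on assumptions. Suppose the response D = E − B has SD 1 and correlates 0.35 with improvement, and the start reaction has SD s and is unrelated to either. The correlation of the planned change with improvement is then r = 0.35/√(1 + s²). With n = 60, power is approximately Φ(atanh(r)·√57 − 1.96).

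| s (assumed) | r | power |
|---|---|---|
| 0 | 0.350 | 0.79 |
| 0.25 | 0.340 | 0.76 |
| 0.5 | 0.313 | 0.69 |
| 0.75 | 0.280 | 0.58 |
| 1.0 | 0.247 | 0.48 |

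The s = 0 row treats a pre-visit segment as noise-free. If that segment carries unrelated noise of SD 0.5, a simple pre-to-end change has r = 0.35/√1.25 = 0.313 and power 0.69, the same as the planned change at s = 0.5. With that noise in both segments, r = 0.35/√1.5 = 0.286 and power is 0.60. None of these inputs is in the documents, so neither the size nor the direction of a power difference is established.

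**The case against.** The strongest reply is that within-visit change is what the protocol set out to study. Hypothesis 3 names its windows, outcome 2 measures exactly that, and pre-visit-to-end is a different quantity. This stands, and it is why the first-to-last change should remain as defined. It does not answer the ambiguity over what that change means.

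A second reply is that the end-of-visit GLM is already free of the start value. This also stands, short of the missing baseline covariate.

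Third, a pre-visit segment may itself be raised by the leads, the camera or anticipation. This stands in part: a short settling time after lead placement helps but cannot guarantee a resting level. What the segment does provide is a reference that contact with the provider has not touched.

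A reader might infer more than the documents support:

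- **That the change has no reference at all.** It has one; what is missing is a reference from before the intervention.
- **That a stated loss of power or excess of false positives is to be expected.** Such figures rest wholly on assumed correlations and SD ratios.
- **That secondary objective 1 falls with this outcome.** It is also served by the synchrony index, which uses no start-to-end change, and by the end-level GLM.
- **That a post-visit segment should become the main measure.** Subjects would then be rating the provider, a different task from the pre-visit forms, and the estimand would change.
- **That the comparison between arms is compromised because the subject is already exposed.** Subjects do not know that two visit types exist, providers are told to keep empathy equal, and the expanded script contains the standard questions. The order of the scripts is in an appendix that is not available here.

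**Conclusion.** The point holds as a limit on interpretation that is cheap to remove. On the text, no GSR or HRV value precedes contact with the provider. The first-to-last change therefore cannot distinguish relaxation from a fading start reaction, and the end-level GLM has no baseline to adjust for. That such a reaction occurs is an inference, supported only by the protocol's own remarks on distress from monitoring and filming; its size is unknown. The consequence is confined to secondary outcome 2 and hypothesis 3. The primary outcome, the sample size and the synchrony index are untouched. If a pre-visit recording is already made in practice, the protocol should say so and the analysis should use it.

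**What to change.** In section 6.2.3 and the section 6.1 schedule, start the patient recording once the leads are attached. After a short settling time, keep a fixed seated segment, for example 5 minutes, before contact with the provider begins, whether in person or by video.

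In section 9.5.2 item 2, add the level in this segment as baseline covariate in the GLM already planned for end-of-visit GSR and HRV against GERD change. Report that result beside the first-to-last-minutes change, which stays as defined. The pre-visit segment will also allow the start reaction, S − B, to be described directly.

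Outcome 2 uses patient recordings only, so pre-visit recording of providers is not needed for it, and neither is a post-visit segment.

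The cost is a few more minutes with leads on, which can overlap with the 15 to 25 minutes of baseline questionnaires already scheduled. Protocol, SAP and consent wording must match, with IRB review, since consent now describes monitoring during the visit. No extra visit, device or staff is required.
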